5.2 Subject Selection

Written informed consent must be obtained prior to the subject undergoing any study-related procedure, including screening tests. All subjects will be required to fulfill the entry criteria listed below

Inclusion Criteria

Subjects who meet all of the following criteria are eligible for enrollment into the study:

1. Subject is capable of providing written informed consent
2. Subject is ≥ 18 years old and ≤ 65 years old
3. Meets at least 4 of 11 modified American College of Rheumatology (ACR) (1997) Revised Criteria for the Classification of Systemic Lupus Erythematosus
4. Has mild to moderate disease activity defined as
 - A minimum SLEDAI score of 2 excluding points for serology (anti-dsDNA antibody and complement)
 - No active renal or nervous system disease
 - No BILAG A in any organ system
 - No expectation by the investigator that corticosteroids will need to be added or doses increased during the 8 week treatment period for any reason
 - No expectation by the investigator that immunosuppressive medication will need to be added or doses increased during the 8 week treatment period
5. Has elevated titers of anti-ds DNA antibody at the time of screening (defined as the titer that meets criteria for “high” in the Core Laboratory at the North Shore/LIJ Health Systems; unequivocal high titer as opposed to borderline, indeterminate or intermediate).
6. Has elevated titers of cross-reactive anti-DNA/DWEYS antibodies at the time of screening (the assays for anti-DNA/DWEYS antibodies will be performed in Dr. [name]’s laboratory; study sites will be notified of results within 3 days of receipt of the samples).
7. If on glucocorticoids, the dose must be ≤ 10 mg daily and stable or decreasing 4 weeks prior to baseline
8. If on immunosuppressive or immunomodulatory medication such as azathioprine, methotrexate, leflunomide, mycophenolate, belimumab or hydroxychloroquine, the dose must have been stable for the 3 months prior to screening, and expected to remain stable over the course of the study.
9. Males and females with potential for reproduction must agree to practice effective birth control measures (2 approved methods of contraception). Nelfinavir can decrease serum levels of oral contraceptives; the slightly increased risk of pregnancy due to an interaction between oral contraception and nelfinavir will be discussed when appropriate and the requirement for a second approved method of contraception will be addressed.

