5.4.1 Study Visits

Screening Visit: Each potential participant will provide written informed consent and no study procedures will be done prior to this. Consenting subjects will participate in a screening visit where assessments will be performed to establish eligibility. The screening visit will include assessments of the following:

- Demographic data
- Medical history, including American College of Rheumatology criteria for SLE
- Physical exam
- Medication review
- Tuberculosis exposure*
- Laboratory assessments:
 - **Central Laboratory:** Serum to be sent overnight to the Coordinating Center at the FIMR. The CSC will be responsible for sending de-identified samples to the [name] Laboratory at the FIMR for anti-DNA/DWEYS antibody testing and to the Core Laboratory in the North Shore LIJ Health System for anti-dsDNA antibody testing. Results will be available to the participating sites within 3 days of receipt at the FIMR. See **MOOP Appendix E** for processing, storing and shipping details.
 - **Local Laboratory** (at the participating site):
 - CBC with differential
 - Comprehensive chemistry
 - C3, C4
 - Urinalysis with micro
 - HIV, Hepatitis B, Hepatitis C
 - Serum β HCG for women of childbearing potential
 - Subjects will be asked to return for a fasting lipid profile
- Disease activity assessments:
 - SELENA SLEDAI
 - BILAG

*All subjects will be tested for latent infection with mycobacterium tuberculosis using the purified protein derivative (PPD) skin test or the Quantiferon Gold test unless 1) they have a history of a positive PPD and have undergone treatment or 2) they have documentation of a negative TB test (PPD or Quantiferon Gold) within the preceding 3 months from screening. PPD will be administered subcutaneously and subjects will be asked to return for the PPD reading in 48-72 hours as per PPD guidelines. If preferred, the Quantiferon Gold test can be sent instead of the PPD. All subjects with a positive PPD or Quantiferon Gold test that have not previously received a full course of treatment are excluded from this study (see exclusion criteria). If a subject has received the BCG vaccine and the PPD test is equivocal, the investigator may choose to use the quantiferon gold test. Subjects with positive PPD or quantiferon gold tests who have not previously been treated for TB will be referred for further evaluation (e.g. including chest X-ray and sputum culture and smear).

Day 1 (initiation of treatment):

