NSAIDS and Tylenol should be held overnight or for 12 hours prior to the assessments on Day 1. The following assessments will take place on Day 1 prior to dosing with the study medication for those subjects who meet eligibility criteria *and are returning for the Day 1 visit more than 10 days after the screening visit:*

- Medical history
- Adverse event review
- Physical exam
- Medication review
- For women of childbearing potential a urine pregnancy test must be negative prior to dosing with study medication
- Laboratory assessments prior to dosing with study medication
 - **Local Laboratory** (at the participating site)
 - CBC with differential
 - Comprehensive chemistry, amylase, lipase
 - C3, C4
 - Urinalysis with micro
 - **Central Laboratory** (see **MOOP Appendix E** for processing, storage and shipping instructions)
 - anti-dsDNA and anti-DNA/DWEYS antibody titers,
 - antibodies to Sm, RNP, Ro, La, anticardiolipin antibodies: IgG, IgA, IgM
 - cytokine levels
 - interferon signature
 - CRP
- Disease activity assessments:
 - SELENA SLEDAI
 - BILAG
 - Joint count
 - PGA
 - SLICC Damage Index
- Patient Assessments:
 - LupusPRO
 - Patient global assessment (PtGA)

- Dispense 30 days of study drug, nelfinavir

For subjects that meet eligibility criteria returning for the Day 1 visit *within 10 days of the screening visit*, the SELENA SLEDAI assessment obtained at screening should be used as the Day 1 SELENA SLEDAI and a repeat CBC, comprehensive chemistry, C3, C4 and urinalysis with micro will not be performed. The following assessments will be performed for these subjects at the Day 1 visit prior to dosing with the study medication:

- Medical history
- Adverse event review
- Physical exam
- Medication review
- For women of childbearing potential a urine pregnancy test must be negative prior to dosing with study medication
- Disease activity assessments:
 - BILAG
 - Joint count
 - PGA
 - SLICC Damage Index
- Patient Assessments:
 - LupusPRO
 - Patient global assessment (PtGA)
- Laboratory assessments prior to dosing with study medication
 - **Central Laboratory** (see MOOP Appendix E for processing, storage and shipping instructions)
 - anti-dsDNA and anti-DNA/DWEYS antibody titers,
 - antibodies to Sm, RNP, Ro, La, anticardiolipin antibodies: IgG, IgA, IgM
 - cytokine levels
 - interferon signature
 - CRP
- Dispense 30 days of study drug, nelfinavir

Day 7: All subjects will return on Day 7 for the following assessments:

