- Disease activity assessments:
 - SELENA SLEDAI
 - BILAG
 - Joint count
 - PGA
- Patient Assessments:
 - LupusPRO
 - Patient global assessment (PtGA)
- Laboratory assessments prior to dosing with study medication
 - **Local Laboratory** (at the participating site)
 - CBC with differential
 - Comprehensive chemistry, amylase, lipase
 - C3, C4
 - Urinalysis with micro
 - **Central Laboratory** (see **MOOP Appendix E** for processing, storage and shipping instructions)
 - anti-dsDNA and anti-DNA/DWEYS antibody titers,
 - antibodies to Sm, RNP, Ro, La, anticardiolipin antibodies: IgG, IgA, IgM
 - cytokine levels
 - interferon signature
 - CRP

Unscheduled visits: At screening all subjects will be given investigator contact information for 24 hour use in the event of an emergency. At each study visit, all subjects will be reminded to call study personnel and arrange for an “unscheduled” visit immediately if they feel ill in any way or experience or have concerns about their health. Subjects will be evaluated and appropriate interventions will be put into place at the discretion of the investigator. If there has been a change in disease activity and an unscheduled visit occurs more than 10 days after an evaluation for disease activity using the SELENA SLEDAI, an assessment of disease activity using the SELENA SLEDAI should be done including the appropriate tests required to complete the SELENA SLEDAI.

Visit Windows: The visits on Days 7 and 14 allow a one day window on either side. The visits on Days 28, 56 and 84 allow for a 3 day window on either side.

5.4.2 Endpoints:

1. Primary endpoint

The primary endpoint is a mechanistic endpoint: inhibition of anti-dsDNA binding. Inhibition of anti-dsDNA binding will be determined by assessment of: change in anti-ds DNA antibody titers from baseline to Day 56.

Blood obtained for the anti-dsDNA antibody titers on Day 1 before administration of nelfinavir and on Days 14, 28, 56 and 84 will be spun and the serum stored at -20 or -80 degrees at each site. Following completion of Day 56, all of the Central Laboratory samples obtained thus far for each subject (Days 1-56 inclusive) will be batched and sent to the central site at the FIMR.

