This study is exploratory and is not powered to adequately assess efficacy. However, we plan to enroll subjects with mild to moderate disease activity that, in the investigators opinion, will not require additional corticosteroids or immunosuppression for treatment of their disease activity. Five different assessments of disease activity are planned therefore we anticipate that we will be able to detect a trend for efficacy in those treated with nelfinavir. The potential effect of nelfinavir on clinical indicators of disease will be evaluated descriptively. Clinical indicators of disease will include:

- Changes in serum C3 and C4 complement levels from baseline to Day 56;
- Changes in serum CRP from baseline to Day 56;
- Changes in the SELENA SLEDAI score from baseline to Day 56;
- Changes in the PGA from baseline to Day 56;
- Changes in from baseline to Day 56;
- Changes in Joint Count from baseline to Day 56;
- Changes in BILAG scores from baseline to Day 56.

c) Health related quality of life

The potential effects of nelfinavir on patient quality of life will be assessed by changes in patient reported outcome measures from baseline to Day 56. The quality of life measures for this clinical trial include the following:

- The LupusPro Health Survey is a validated patient reported measure of functional health and well-being generalizable across ethnic backgrounds and gender [37].
- The patient global assessment scale is a 10 cm visual analogue scale with 1 mm increments from 0 through 100. 0 reflects no disease activity in the patient's assessment and 100 reflects maximum disease activity.

d) Interferon signature

Secondary analyses will explore the potential effect of nelfinavir on the expression of the IFN signature. Changes in expression of IFN inducible genes will be determined from baseline to Day 56. Expression of IFN inducible genes will be determined in two ways:

- Transfer of the IFN signature: as described previously [38], serum from SLE subjects will be incubated with normal PBMC and expression of IFN inducible genes will be measured using reverse transcriptase PCR.
- Microarray analysis: Expression of IFN inducible genes in peripheral blood will be measured by microarray analysis of RNA (extracted from whole blood in the PaxGene tubes) using the Illumina HT12v4 platform.

e) Cytokines

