Changes in serum cytokine levels (IL-1, IL-6, and TNF α) from baseline to Day 56 will be determined for each treatment group at each dose level using ELISA assays in [name] laboratory.

f) Serology/Anticardiolipin Antibody Binding

Assessment of changes in autoantibody binding, including anti-Ro, La, Sm, RNP and cardiolipin antibodies, from baseline to Day 56 will be similar to the assessment of anti-dsDNA antibody binding. Investigators and study personnel will be blinded to autoantibody titers drawn during the course of the study. Blood obtained for the autoantibody titers will be spun and the serum stored at -20 or -80 degrees at each site on Days 1, 14, 28, 56 and 84. Frozen sera for the Central Laboratory for Days 1-56 will be sent overnight to the Coordinating Center following the Day 56 visit for each subject for determination of the primary endpoint. At study completion, all of the Day 84 Central Laboratory samples will be batched and sent to the Feinstein Institute. The samples will then be run simultaneously in the core laboratory in the North Shore/LIJ Health System.

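### The SELENA SLEDAI change to Day 56 includes an anti-dsDNA item that is known at entry but has no current result at on-treatment visits, and no scoring rule covers it, so the change can be distorted in either direction.

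*Combined protocol and SAP*

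**What the plan says.** **Endpoint.** Section 5.4.2(b) names "Changes in the SELENA SLEDAI score from baseline to Day 56" among the clinical indicators of disease, to be evaluated descriptively. It sets no serology points aside.

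**Eligibility.** Section 5.2, inclusion 4, does set them aside: "A minimum SLEDAI score of 2 excluding points for serology (anti-dsDNA antibody and complement"). Section 5.1 has the same exclusion. Inclusion 5 requires that each subject "Has elevated titers of anti-ds DNA antibody at the time of screening", defined as an unequivocally high result.

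**What the site knows at entry.** Of the central screening assays, section 5.4.1 says: "Results will be available to the participating sites within 3 days of receipt at the FIMR". For a Day 1 visit within 10 days of screening, "the SELENA SLEDAI assessment obtained at screening should be used as the Day 1 SELENA SLEDAI". For a later Day 1, the SELENA SLEDAI is repeated.

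**What the site knows on treatment.** The SELENA SLEDAI is scored at Days 28 and 56. The local tests at those visits include C3 and C4 but not anti-dsDNA. Under section 5.4.2, once the Day 56 visit is done, "all of the Central Laboratory samples obtained thus far for each subject (Days 1-56 inclusive) will be batched and sent to the central site", and the Day 1, 14, 28 and 56 sera are then assayed together. Section 5.4.2(f) adds: "Investigators and study personnel will be blinded to autoantibody titers drawn during the course of the study". It makes no exception for disease-activity scoring.

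**Unscheduled visits.** If disease activity has changed and the last score is more than 10 days old, "an assessment of disease activity using the SELENA SLEDAI should be done including the appropriate tests required to complete the SELENA SLEDAI".

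**The concern.** A change score is interpretable only if both ends are built from the same items. Here the schedule, the blinding and the endpoint definition, each followed as written, allow a baseline that counts the anti-dsDNA item and a Day 56 score that has no current result for it. Sites must still enter something, and the documents do not say whether the item is set to zero, carried forward, omitted or completed later. Different sites may choose differently.

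Two secondary objectives concern disease activity: that it does not increase, and that it decreases. Section 5.4.2(a) also uses disease activity for safety. There is no placebo arm in which a scoring artefact could cancel, so a fall caused by an unscored item would look like improvement, or could offset a real worsening.

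**Working it through.** The plan gives no expected SLEDAI change, standard deviation or power, so there is no figure to reproduce. The check traces the scoring path and then sizes the distortion.

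**Step 1: scoring path** (sections 5.2, 5.4.1, 5.4.2)

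| Visit | SELENA SLEDAI | Anti-dsDNA result available to the site |
|---|---|---|
| Screening | Scored | High by inclusion 5; reported within 3 days of receipt |
| Day 1, within 10 days | Screening score reused | Screening result known |
| Day 1, more than 10 days | Scored again | Screening result only; Day 1 serum stored unassayed |
| Day 28 | Scored | No current result |
| Day 56 | Scored | No current result; sera shipped afterwards |
| Day 84 | Scored | No current result; sera shipped at study completion |

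Complement can be scored on site at Days 28, 56 and 84. Anti-dsDNA cannot be scored from a current result.

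**Step 2: inputs for size**

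- w, the weight of the anti-dsDNA item. The documents show that it carries points but not how many. Assumption: w = 2, range 1 to 4.
- f, the share of subjects with the item counted at baseline and scored zero at Day 56. It is not in the documents; range 0 to 1.
- g, the share whose item would truly become negative by Day 56. It is not in the documents; range 0 to 1.

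**Step 3: effect of each convention**

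- *Scored zero on treatment, with nothing truly changed.* Spurious mean change = -w × f. With w = 2: f = 0.25 gives -0.5, f = 0.5 gives -1.0, f = 0.75 gives -1.5 and f = 1 gives -2.0 points. At f = 1 the figure is -1 for w = 1 and -4 for w = 4.
- *Screening value carried forward.* The recorded item change is 0 and the true one is -w × g, so the distortion is +w × g and a real fall is hidden. With w = 2 this runs from 0 to +2 points.
- *Missing at both ends.* The item contributes 0 to baseline and to Day 56, so the distortion is 0.

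**Step 4: scale for one subject.** At the entry minimum of 2 clinical points, with no complement points, the baseline total is 2 + w. The item's share is w/(2 + w): 1/3 = 33% for w = 1, 2/4 = 50% for w = 2 and 4/6 = 67% for w = 4.

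**Step 5: after a common rule.** If the item is omitted at every visit, or completed at every visit from the batched assay, f = 0 and the spurious change is 0. With central completion, a fall in the item is a real titre change, but it then overlaps with the primary endpoint. Omission removes the overlap as well.

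**The case against.** A sponsor could fairly reply as follows.

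- *A high screening titre is not a scored baseline item.* This stands. When Day 1 is more than 10 days after screening, the score is repeated without a current titre, so the item may be absent at both ends and cancel. A reader might infer that every subject scores the item at baseline and then loses it, so that a 2-point fall is built in. The documents do not support that: they give neither the split by time from screening nor the scoring convention.
- *The data exist.* This also stands. The Day 1 to 56 sera are assayed after each subject's Day 56, so a complete score could be assembled. Nothing in the protocol says that it will be.
- *The scoring rule may be in the Manual of Procedures.* Section 5.4 places the schedule of events there, and that manual is not among the documents. The rule could be there, but an endpoint's definition belongs in the protocol.
- *The objectives do not depend on this score alone.* Correct. BILAG, the PGA and joint count are also listed, and section 8.1 defines flare by BILAG. It would be too strong to say that the disease-activity objectives rest on the SLEDAI change.
- *A full index that includes serology is a legitimate choice.* Agreed. A reader might infer that a responder on the primary endpoint automatically improves on SLEDAI. Response is a reduction of at least 35%, not normalisation, and nothing shows that such a subject would lose the item. The overlap is a reason to prefer a serology-free score, not proof of circularity.

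What remains is that the plan, followed as written, permits non-comparable ends, and no control arm would reveal it.

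**Conclusion.** The point holds as a defect in how one secondary endpoint is defined. Distortion is possible but not certain, and its direction depends on a convention that the plan does not state. On the assumed 2-point weight, the spurious mean change lies between 0 and -2 points if the item is scored zero on treatment; over weights of 1 to 4 the extreme is -1 to -4. Carry-forward errs the other way. These sizes rest on w, f and g, none of which the documents give.

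The analysis is descriptive, the study is described as not powered for efficacy, and the primary Simon two-stage decision does not use this score. The change should be made, but the trial's main conclusion does not hang on it.

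**What to change.** In section 5.4.2(b), define the endpoint as change in SELENA SLEDAI without the anti-dsDNA item, derived in the same way at baseline and at Days 28, 56 and 84. The score in inclusion 4, which also drops complement, is a ready-made version. Dropping complement is optional, because C3 and C4 are measured locally at those visits.

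Report the full score as a supplement, with the anti-dsDNA item completed centrally from the batched assay at all visits, including Day 1 whether or not the screening score was reused.

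Reconcile the unscheduled-visit text in section 5.4.1, which calls for the tests needed to complete the score, with the blinding statement in section 5.4.2(f). Which local tests an investigator may order is a clinical matter and is not addressed here.

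The cost is a few sentences and one derived variable, with no new samples or visits. The small downside is that the main score is no longer the full standard index; the supplementary score covers that.

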6. STUDY WITHDRAWAL OR DISCONTINUATION

6.1 Discontinuation of Protocol-Specified Treatment Requirements

A subject is considered to have completed the study when he/she has completed the Day 84 visit. Protocol-specified requirements for the treatment of subjects will be discontinued for subjects under the following conditions:

1. Any protocol-specified treatment requirement will be discontinued immediately at any time during the study at the request of the subject.
2. Investigator will discontinue any protocol-specified treatment requirement if the subject's health, safety, and/or well-being is threatened.
3. Protocol-specified treatment requirements will be discontinued and replaced with appropriate therapy for any subject who experiences or requires any of the following:
 - An increase in dose of any concurrent SLE medications (including but not limited to corticosteroids, immunosuppressives, and/or immunomodulatory medications such as azathioprine, methotrexate, leflunomide, mycophenolate, and/or hydroxychloroquine) or addition of a new immunosuppressive medication (including cyclophosphamide or rituximab). *Note:* corticosteroids may be increased for a maximum of 2 days for reasons unrelated to SLE disease activity provided the last dose is taken more than 5 days prior to the day 56 assessments (section 5.3)
 - A grade 3 or higher NCI-CTCAE (version 4.0) adverse event that is considered to be related to study therapy during the course of the study. The exception to this will be hemoglobin levels where a grade 3 level of 8 may be acceptable. This will depend on the hemoglobin level at study entry and the investigator's assessment of relationship to study drug. A requirement for blood transfusion would be considered a stopping point.
 - Pregnancy
 - If a subject enrolls in a concurrent interventional trial.

In addition, subject non-compliance with treatment regimens or failure to keep appointments may disrupt protocol-specified treatment requirements and necessitate permanent discontinuation of treatment procedures at the discretion of the investigator.

Finally, protocol specified treatment requirements will be discontinued as a natural consequence in subjects who are withdrawn from the study per the study guidelines.

